2.10.4 Immune cell characterization in peripheral blood and bone marrow

Peripheral blood and bone marrow derived mononuclear cells will undergo immunologic assessments to assess the impact of therapy on general measures of cellular immunity. We will determine the number of immune cells (T-reg, CD4 effector T cells, CD8 T-reg, CD8 effector T cells, NK, NKT, B cells, MSCs, M1 and M2 macrophages, Dendritic cells and MDSCs at screening and during therapy. These cells will be quantified using CyTOF. Each cell type will be defined by unique combinations of antibodies based on previous publications^{59,60}. Regulatory T cells will be defined as CD4/CD25/FOXP3+ cells. Levels of naïve, effector and central memory cells will be quantified as CD45RA, CD45RO/CD62L-/CD27- and CD45RO/CD62L+/CD27+ cells, respectively. NK cells will be quantified by expression of CD56+ subsets. MDSCs will be quantified by CD33+/lineage-/DR- and CD11b/lineage-/DR- cells. We will also examine the percent expression of checkpoint regulators and how they are modulated with therapy. These checkpoint regulators include PD-1, Lag-3, Tim-3 and CTLA-4.

2.10.5 RNA sequencing of immune cells during therapy

We will dissect molecular alterations that occur in these cells during progression in MM and the role of therapy on these cells. We will obtain the T-reg, NK cells and MDSCs from the peripheral blood and bone marrow at the same time points described above. Similar samples will be obtained from the comparative untreated cohort. The cells will be isolated by flow sorting using single cell sequencing and submitted for RNA sequencing as described above. Single cell sequencing of immune cells has recently shown significant advances in understanding immune regulation of the tumor microenvironment. Therefore, we believe that these studies will help define the immune microenvironment in smoldering MM before and after therapy with a PD-1 inhibitor.

2.10.6 Cell free DNA to monitor genomic evolution

Human cancers are caused by the accumulation of genetic alterations in cells. Of special importance is the sequence at which the genetic events arise, as early events likely result in common oncogenic dependency that represents favorable therapeutic targets. Non-invasive liquid biopsies, by means of circulating tumor cells (CTC) and circulating free DNA (cfDNA),

CONFIDENTIAL

This document is confidential. Do not disclose or use except as authorized.

facilitate the continuous monitoring of genomic evolution. CTCs have been identified in solid tumors as well as in multiple myeloma (MM). Likewise, massive parallel sequencing of cfDNA has been shown to track genomic evolution of several types of cancer during the course of the disease. This could potentially complement current invasive biopsy approaches and constitute a new paradigm for monitoring clonal evolution in human cancers and provide the possibility for an early detection of known MM driver mutations that could predict risk of progression. CfDNA sequencing can be challenging because of the small fragment size of DNA in the peripheral blood (around 166bp), the low yield of DNA and the usual low allelic fraction of tumor-derived DNA among the cfDNA. Therefore, we developed two different approaches to sequence cfDNA. After high-speed centrifugation of frozen samples, to eliminate residual cells from plasma, cfDNA is extracted using the Qiagen circulating nucleic acid kit. As little as 5ng of cfDNA is then subjected to library preparation using the Kapa HyperPlus kit, which enables us to prepare libraries from small DNA fragments and minimal DNA yield. CfDNA libraries are qualified for further sequencing using ultra-low-pass whole genome sequencing (ULP-WGS). The ULP-WGS is a low cost approach developed by the Blood Biopsy Group to nominate samples containing sufficient fraction of tumor-derived DNA for whole exome sequencing (WES). Large numbers of cfDNA libraries are multiplexed and sequenced to an average of 0.1X genome-wide sequencing coverage. Samples with lower than 5% purity, not suitable for WES, are analyzed by a targeted deep sequencing approach for cfDNA to increase the sensitivity of detection of low allelic fraction mutations. Our custom amplicon set includes 109 genes exons to detect single nucleotide variants (SNVs). WES and targeted libraries are then sequenced on a HiSeq 4000. Mutations are called using MuTect in single-sample mode. All known germline variants are filtered out (1000 Genome Project Consortium release 2.2.2) and somatic SNVs are characterized for their presence in the Catalogue of Somatic Mutations in Cancer (COSMIC) database. All somatic SNVs are reviewed manually with Integrative Genomic Viewer (IGV) to validate their accuracy. We assess the reproducibility of our assay by running samples in duplicates, which show a high correlation between the 2 replicates in the same test run.

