The tumor research samples will be collected at the time of scheduled bone marrow biopsies. From these samples, high quality DNA (for tumor cells) and RNA for both exome sequencing and RNA sequencing will be obtained. In brief, BM aspirates will be obtained after informed consent. The tumor cells will be collected using CD138+ bead selection (over 90% purity based on prior publications)^{30,31}. For samples that have a small fraction of plasma cells, we will use flow sorting for CD138/CD38/CD56 and CD19-ve to obtain a pure malignant plasma cell population based on prior published markers of malignant plasma cells⁴⁸. Germline DNA will also be obtained from a buccal swab from all patients.

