2.10.2 Exome sequencing of tumor cells

Whole-exome capture libraries will be constructed from 100ng of tumor and normal DNA followed by shearing, end repair, phosphorylation and ligation to barcoded sequencing adapters. The DNA will be size-selected to exonic hybrid capture using SureSelect v2 Exome bait (Agilent, CA). Samples will be multiplexed and sequenced on Illumina HiSeq flowcells with the goal of an average depth of coverage of 100x. The resulting data will be analyzed with the current Illumina pipeline, which generates data files (BAM files). The details of the current analysis pipeline are published elsewhere^{30,49}. Briefly, somatic single nucleotide variants are determined using the MuTect algorithm⁵⁰. Indels and translocations are determined by the algorithms IndelLocator and dRanger, respectively. The MutSig algorithm identifies genes in which the observed mutations are inconsistent with what would be expected at random⁵¹. To accurately assess the significance of mutations, MutSig takes into account several covariates, which influence the background mutation model. These include the expression level of genes (for which published gene expression data of MM samples can be used), and other gene characteristics observed empirically to co-vary with mutation rate: local relative replication

CONFIDENTIAL

This document is confidential. Do not disclose or use except as authorized.

time⁵², and open vs. closed chromatin status⁵³. Focal as well as arm-level copy number variations will be determined based on whole exome sequencing and subsequent application of the GISTIC algorithm⁵⁴.

2.10.3 RNA sequencing of tumor cells.

For RNA Sequencing, poly-A selection and cDNA synthesis will be performed, followed by library preparation, sequencing (76bp or 101bp paired reads), and sample identification with quality control. Details of experimental design are described in^{55,56-58}. We will perform library construction using a non-strand specific Illumina TruSeq Protocol and sequence coverage to 100M total reads. Analysis will be performed as described in the preliminary data and in previous studies⁵⁶⁻⁵⁸.

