9. BIOMARKER, CORRELATIVE, MRD ASSESSMENT AND SPECIAL STUDIES

The mandatory correlative studies will consider several potential predictive biomarkers. As discussed in the appropriate sections of the protocol, mutations such as N-RAS, K-RAS, MYC up-regulation, and gain or loss of chromosome 1q or 1p are hypothesized to correlate with disease progression. The sample size of this phase-2 study, 41 patients, will allow exploratory analyses on TTP correlation with biomarkers. The number of biomarkers and the associated

CONFIDENTIAL

This document is confidential. Do not disclose or use except as authorized.

multiplicities will only allow us to provide empirical point estimates and confidence intervals for TTP-biomarker concordance indexes.

Please refer to Appendix B for a full sample collection table. This trial will provide samples from consenting SMM patients treated with Nivolumab, lenalidomide and dexamethasone to comprehensively characterize the MM genome and immune cells function and define molecular events driving development and progression of MM.

We will attempt to obtain samples on all patients at several time points during the study, including before therapy, at the end of cycle 6, at the time of response determination (CR), at disease relapse, and at the time of completion of the study. It is anticipated that approximately 90% of samples collected will be adequate for sequencing studies proposed.

The tumor cells will be collected as described below. From these samples, high quality DNA (for tumor cells) and RNA (for tumor cells and immune cells) for both exome sequencing and RNA sequencing will be obtained. Germline DNA will be also obtained from a buccal swab from all patients at any time point of the study. Samples collected for the purpose of research at Dana Farber Cancer Institute will be banked and retained for research use indefinitely.

Peripheral blood and bone marrow derived mononuclear cells will undergo immunologic assessments to assess the impact of therapy on general measures of cellular immunity, MM reactive T cells, and antigen specific immunity. The percentage of circulating and bone marrow derived regulatory immune cells will be determined.

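### Cell-free DNA mutations are called without the patient's own germline sample, so rare inherited variants can be kept as somatic calls

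*Combined protocol and SAP*

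**What the plan says.** Section 2.10.6 describes the cfDNA pipeline. Tumor fraction is first estimated by ultra-low-pass whole-genome sequencing. Samples with enough tumor DNA go to whole-exome sequencing (WES), and the rest go to a 109-gene amplicon panel: "Samples with lower than 5% purity, not suitable for WES, are analyzed by a targeted deep sequencing approach". The calling rule is then "Mutations are called using MuTect in single-sample mode".

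Three steps follow:

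- Germline removal: "All known germline variants are filtered out (1000 Genome Project Consortium release 2.2.2").
- Annotation: "somatic SNVs are characterized for their presence in the Catalogue of Somatic Mutations in Cancer (COSMIC) database".
- Manual check: "All somatic SNVs are reviewed manually with Integrative Genomic Viewer (IGV) to validate their accuracy".

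The section also mentions duplicate runs to assess reproducibility. It does not mention the patient's own germline DNA.

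Elsewhere that DNA is planned for. Section 2.10.1 says "Germline DNA will also be obtained from a buccal swab from all patients", and Section 9 repeats it: "Germline DNA will be also obtained from a buccal swab from all patients at any time point of the study". The study calendar (Section 10) and Appendix B schedule the collection, and Appendix B allows an Oragene kit instead of swabs. For the marrow exome, Section 2.10.2 says "Whole-exome capture libraries will be constructed from 100ng of tumor and normal DNA".

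**The concern.** A caller run on one sample cannot tell an inherited variant from an acquired one by comparison, so the separation rests on the later filters. The named filter removes variants that a public catalogue lists. An inherited variant that is not listed passes it, and the plan's own wording then places it among the somatic SNVs.

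The examination of molecular evolution in the tumor cells is a secondary objective (Section 1.5), and Section 2.10.6 offers cfDNA as a way to follow that evolution over time and detect driver mutations early. Appendix B draws a cfDNA (Streck) tube at baseline, on Day 1 of Cycles 1 to 12, at confirmation of complete response, and at end of treatment or progression. A patient who completes treatment therefore gives at least 1 + 12 + 1 = 14 samples. An inherited variant that passes the filter can recur along that series and be read as a clone that therapy does not clear.

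**Working it through.** The documents give no error rate, sample size or expected number of calls for cfDNA, so there is no stated figure to reproduce. The check has three parts.

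**1. Does any stated step remove an unlisted inherited variant?**

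| Step in Section 2.10.6 | Effect on an unlisted inherited variant |
|---|---|
| 1000 Genomes filter | None: the variant is not in the file |
| COSMIC | None stated: it describes calls already named somatic and is not given as an exclusion rule |
| Manual IGV review | Uncertain: the aim is accuracy, and no germline or allele-fraction criterion is given. An inherited variant is a genuine variant and can pass |
| Duplicate runs | None: an inherited variant reproduces in both replicates |

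No later section adds a matched-normal step for cfDNA.

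**2. Can an inherited variant plausibly be missing from a reference file?**

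For a variant of population allele frequency f and a panel of N people (2N chromosomes, independent draws from the same population), P(absent) = (1 − f)^(2N). The documents give neither N nor f; the values below are assumptions that show a range.

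| f | N = 1,000 | N = 2,500 | N = 10,000 |
|---|---|---|---|
| 0.00001 | 0.98 | 0.95 | 0.82 |
| 0.0001 | 0.82 | 0.61 | 0.14 |
| 0.001 | 0.14 | 0.007 | about 0 |

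Very rare variants usually pass at every panel size shown. Variants at 1 in 1,000 or above are mostly caught. The gap is therefore confined to rare and private variants.

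**3. Would the allele fraction give it away?**

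In a diploid region a clonal heterozygous tumor mutation has expected allele fraction purity/2. A heterozygous inherited variant has about 0.5.

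| Purity | Tumor mutation, purity/2 | Inherited | Ratio |
|---|---|---|---|
| 5% | 0.025 | 0.5 | 0.5/0.025 = 20 |
| 10% | 0.05 | 0.5 | 0.5/0.05 = 10 |
| 20% | 0.10 | 0.5 | 0.5/0.10 = 5 |
| 50% | 0.25 | 0.5 | 0.5/0.25 = 2 |
| 90% | 0.45 | 0.5 | 0.5/0.45 = 1.1 |

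Near the 5% limit, and in the panel samples below it, an inherited variant stands far outside what a diploid heterozygous tumor clone could produce. As purity rises the two converge. Allele fraction would thus be a usable screen at low purity and a poor one at high purity, and the plan states no such rule at either end.

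The diploid assumption also matters. Table 2 in Section 2.3 gives 13q deletion in 35–50% of SMM and hyperdiploidy in 40–50%. In altered regions the inherited fraction moves away from 0.5 and shifts with tumor fraction, so a constant value near one half is not a dependable marker either.

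**The case against.** The strongest reply has four parts.

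- **Every call is reviewed by hand.** This is true and it matters. With tumor fraction already estimated, an alert reader would question a 50% variant in a sample known to be 5% tumor. The section itself says that tumor DNA is usually a small part of cfDNA, so many samples may fall in this easy range. What remains is that the review has no written germline criterion, and at high purity the allele fraction does not help.
- **Recurrence in every serial sample hints at germline origin.** It does, but a truncal tumor mutation recurs too, and no rule says how to decide between them.
- **The text is background.** Section 2.10.6 sits under the correlative background and describes an assay already in use. Section 13 attaches no cfDNA estimand, test or threshold, and Section 9 limits biomarker work to exploratory estimates. This stands and limits the importance of the point. Molecular evolution is also served by serial marrow sequencing, for which normal DNA is already planned.
- **A matched normal may be unavailable.** Section 9 expects about 90% of samples to be adequate for sequencing, and swabs may be taken at any time. This calls for a fallback; it is no reason to leave the normal unused when it exists.

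A reader might infer more than the documents support. They do not show that inherited variants will be scored as tumor mutations as a rule, because the manual review may catch some. Nor do they show that such variants mask real change: SNVs are called one by one, and a flat inherited variant does not hide the rise or fall of another. The 10- to 20-fold gap at 5–10% purity is not a measure of harm; it makes the error easier to see.

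**Conclusion.** The point holds as a minor one. The stated cfDNA pipeline can keep rare inherited variants as somatic SNVs, although the germline material needed to prevent this is already being collected. The risk of confusion is greatest at higher tumor fraction (25% or 45% expected for a clonal tumor mutation at 50% or 90% purity, against about 50% inherited) and small near 5% purity (2.5%).

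The frequency cannot be stated: the documents give neither the number of unlisted inherited variants per patient nor the size of the reference file. The allele fractions assume clonal, heterozygous mutations in diploid regions. The conclusion also assumes that the IGV review applies no unwritten germline rule; if it does, or if matched calling is already intended, this becomes a documentation gap that one sentence closes.

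The effect stays within the exploratory cfDNA part of the molecular-evolution objective. The 2-year progression-free endpoint, its decision rule and the safety rule are unaffected.

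**What to change.** In Section 2.10.6:

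- Call cfDNA exomes in tumor-normal mode against the same patient's germline exome, and name the buccal (or Oragene) sample as that normal. Section 2.10.2 plans normal libraries without naming their source.
- For the 109-gene panel, remove variants present in that germline exome wherever it covers the panel target.
- Where there is no usable normal or no coverage, keep single-sample calling with the catalogue filter, then flag those calls and report them separately.
- Write down the germline criterion that the manual review applies, including how tumor fraction is used.

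The cost is mainly re-analysis: no new visit or specimen type is needed. There are two limits. Some patients may lack a usable or timely swab: if the 90% adequacy figure applied to swabs, which is an assumption, that would be about 41 × 0.10 ≈ 4 of the planned 41. Collection at any time allows some to be recovered. Section 2.10.6 also does not name the cfDNA exome capture, so its overlap with the SureSelect v2 targets of Section 2.10.2 must be checked first.

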3. PARTICIPANT SELECTION

3.1 Eligibility Criteria

3.1.1 Age \geq 18 years.

3.1.2 Must meet criteria of high risk smoldering MM based on the criteria described below:

Definition of high-risk SMM:

- Bone marrow clonal plasma cells \geq 10% and \leq 60% **and any one or more of the following:**
 - Serum M protein \geq 3.0g/dL (IgA, IgG, IgM, or IgD)
 - IgA SMM
 - Immunoparesis with reduction of two uninvolved immunoglobulin isotypes
 - Serum involved/uninvolved free light chain ratio \geq 8 (but

CONFIDENTIAL

This document is confidential. Do not disclose or use except as authorized.

less than 100)

- Free Light Chain Smoldering Myeloma patients as defined in section 2.4 are not excluded
- Progressive increase in M protein level (Evolving type of SMM)
 - Increase in serum monoclonal protein by $\geq 10\%$ on two successive evaluations within a 6 month period
- Bone marrow clonal plasma cells 50-60%
- Abnormal plasma cell immunophenotype ($\geq 95\%$ of bone marrow plasma cells are clonal) and reduction of one or more uninvolved immunoglobulin isotypes
- t (4;14) or del 17p or 1q gain
- Increased circulating plasma cells
- MRI with diffuse abnormalities or 1 focal lesion
- PET-CT with one focal lesion with increased uptake without underlying osteolytic bone destruction
- Urine monoclonal light chain excretion ≥ 500 mg/24 hours

3.1.3 ECOG Performance Status (PS) 0, 1, or 2 (Appendix A)

3.1.4 The following laboratory values obtained ≤ 21 days prior to registration and confirmed prior to the first dose of study drug:

- ANC $\geq 1000/\mu\text{L}$
- PLT $\geq 50,000/\mu\text{L}$. Platelet transfusions to help patients meet eligibility criteria are not allowed within 3 days before study enrollment.
- Total bilirubin ≤ 1.5 mg/dL (If total is elevated check direct and if normal patient is eligible.)
- AST $\leq 3 \times$ institutional upper limit of normal (ULN)
- ALT $\leq 3 \times$ institutional upper limit of normal (ULN)
- WBC $\geq 2000/\mu\text{L}$

3.1.5 Ability to understand and willingness to sign a written informed consent before performance of any study-related procedure not part of normal medical care, with the understanding that consent may be withdrawn by the subject at any time without prejudice to future medical care.

CONFIDENTIAL

This document is confidential. Do not disclose or use except as authorized.

3.1.6 Female patients who are postmenopausal for at least 1 year before the screening visit or are surgically sterile. Females of childbearing potential* must have a negative serum or urine pregnancy test with a sensitivity of at least 25 mIU/mL within 10 – 14 days and again within 24 hours prior to prescribing lenalidomide for Cycle 1 (prescriptions must be filled within 7 days as required by Revlimid REMS®) and must either commit to continued abstinence from heterosexual intercourse or begin TWO acceptable methods of birth control, one highly effective method and one additional effective method AT THE SAME TIME, at least 28 days before she starts taking lenalidomide. Females of reproductive potential must agree to follow instructions for method(s) of contraception for the duration of treatment with any study drug(s) plus 5 half-lives of study plus 30 days (duration of ovulatory cycle) for a total of 120 days after their last dose of lenalidomide (Revlimid). Women must not breastfeed.

Female patients who are of childbearing potential must use contraception for 5 half-lives plus 30 days after their last dose of nivolumab for a total of 5 months.

* *A female of childbearing potential is a sexually mature female who:*

- *Has not undergone a hysterectomy (the surgical removal of the uterus) or bilateral oophorectomy (the surgical removal of both ovaries) or*
- *Has not been naturally postmenopausal (amenorrhea following cancer therapy does not rule out childbearing potential) for at least 24 consecutive months (i.e., has had menses at any time during the preceding 24 consecutive months)*

3.1.7 All study participants must be registered into the mandatory Revlimid REMS® program, and be willing and able to comply with the requirements of the REMS® program.

3.1.8 Females of reproductive potential must adhere to the scheduled pregnancy testing as required in the Revlimid REMS® program.

3.1.9 Men must agree to use a latex condom during sexual contact with a female of childbearing potential even if they have had a successful vasectomy during the entire study treatment period and through 154 days after the last dose of lenalidomide (Revlimid) or agree to practice true abstinence when this is in line with the preferred and usual lifestyle of the subject. (Periodic abstinence [eg, calendar, ovulation, symptothermal, post-ovulation methods] and withdrawal are not acceptable methods of contraception.)

Men who are sexually active with women who are of childbearing potential must adhere to contraception for a period of 5 half-lives plus 90 days for a

CONFIDENTIAL

This document is confidential. Do not disclose or use except as authorized.

total of 7 months after their last dose of nivolumab.

